6. STUDY PATIENTS

Unless otherwise specified, all tables in this section will be presented by the treatment regimen groups described in Section 5.1.1.1.

6.1. Disposition of Patients

Patient disposition will be summarized for the All-Enrolled Analysis Set. This table will present the number of patients in the Full Analysis Set (FAS), the number of patients with an efficacy period, the number of patients in the Safety Analysis Set and the number of patients in the Surgery Subgroup. The number and percentage of patients who completed/discontinued the study, including the primary reason for those who discontinued, will be tabulated. This table will be presented by treatment regimen and for the inhibitor subgroups, as described in Sections 5.1.1.1 and 5.1.1.2 respectively.

Patient disposition, including the date of the last visit and the reason for early termination or early withdrawal for patients who did not complete the study, will be provided in a data listing.

The number and percentage of patients enrolled will be summarized by country and site, for the All-Enrolled Analysis Set.

The number of patients attending each key study visit will be summarized by key study visit overall for the Safety Analysis Set, including visits in the main study. This analysis will also be performed for the ITI Analysis Set, including only visits in the ITI period.

6.2. Demography and Baseline Disease Characteristics

Demographics and baseline characteristics will be summarized for the Safety Analysis Set. Demographics and baseline characteristics will be summarized as continuous variables and as categorical variables, as appropriate.

6.2.1. Demography

Demographic characteristics include age, height and weight at screening plus sex, race, ethnicity, and geographic location. Geographic locations are defined as Europe, North America, and other. Europe includes France, Germany, Ireland, Italy, the Netherlands, Poland, Spain, Sweden, and the United Kingdom. North America includes Canada and the United States. Other countries include Australia, Brazil, and New Zealand.

Age will be obtained from the interactive voice and web response system (IXRS) to avoid calculation errors arising from not having the day of the month for birth dates in the eCRF. Age will be summarized both as a continuous variable using descriptive statistics and categorically with the age categories representing each year from <1 through 5. This table will be presented by treatment regimen and for the inhibitor subgroups, as described in Sections 5.1.1.1 and 5.1.1.2 respectively.

6.2.1.1. General Medical and Surgical History

Medical and surgical history will be summarized by body system. A patient is counted only once if they report more than one occurrence in the same body system.

6.2.2. Baseline Disease Characteristics

6.2.2.1. Hemophilia History

Time since diagnosis of hemophilia will be summarized with descriptive statistics. The screening FVIII activity values will be summarized categorically (<1%, ≥1%). Categorical summaries will also be provided for FVIII genotype, family history of inhibitors, vaccination within last year, HIV status, Hepatitis B status, and Hepatitis C status.

6.2.2.2. Bleeding History

Patients' total estimated bleeding episodes (spontaneous plus traumatic) within the last 3 months prior to study screening will be summarized categorically (0, 1-2, 3-5 and >5 and with descriptive statistics). Percentages for the categorical summaries will be based on the number of patients who provided data. Total estimated bleeding episodes in the 3 months prior to study screening will also be summarized for the number of spontaneous and traumatic bleeding episodes using descriptive statistics.

6.2.2.3. Family Hemophilia History

No family history of hemophilia is collected in this study. Family history of inhibitors to FVIII is referenced above in Section [6.2.2.1](#).

6.2.2.4. Risk Factors for Inhibitor Development

The following risk factors will be summarized for patients in the inhibitor subgroup and those not, as specified in Section [5.1.2.5](#):

- Race - black or African American or white Hispanic / other, from demography data
- Family history of inhibitor - Y/N, as per hemophilia history data
- Vaccination - Y/N, as per hemophilia history data and concomitant medications prior to date of inhibitor development
- FVIII genotype - to be delineated based upon final data according to the following guidelines for all genotypes that fall under the general categories of:
 - High risk - large deletions or nonsense variants
 - Medium risk – splicing variants or inversions of intron 1 and intron 22
 - Low risk - small deletions/insertions or missense variants
 - Unknown/missing

- TEAE of infection prior to date of inhibitor development - Y/N, derived from adverse event data based upon events with MedDRA SOC Infections and Infestations
- Major surgery during study prior to date of inhibitor development - Y/N

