### 10.2.3. Prophylaxis Treatment

It is anticipated that subjects will begin a prophylaxis regimen prior to or immediately following the occurrence of a third hemarthrosis (joint bleed). The dose for initiation of prophylaxis may be chosen by the Investigator within the range of 25 to 80 IU/kg. However, based on data from the completed clinical studies, and knowledge of increased clearance of factor concentrates in children <6 years of age, more frequent or higher doses of up to 80 IU/kg may be required to minimize breakthrough bleeding events. The dose can be adjusted based on the subject's response to dosing in the range of 25 to 65 IU/kg at 3 to 5 day intervals. Adjustments to the dose and dosing interval can be made based upon available IR data, subsequent FVIII activity levels, level of physical activity, and bleeding pattern, in accordance with local standards of care for a prophylactic regimen.

Parents/caregivers will be instructed to administer rFVIII Fc at home or to have it be administered by a qualified professional under the direction of the Investigator. Treatment will continue until the subject has reached at least 50 EDs to rFVIII Fc study drug, completed follow up of an ITI regimen, or the end of study is declared, see Section [7.5](#)).

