5.1.1.2. Inhibitor Subgroups

Selected tables will further be presented by the following groups:

- Patients in the inhibitor subgroup (see Section 5.1.2.5)
- Patients not in the inhibitor subgroup

For longitudinal data, the safety or efficacy periods included for these groups is the entire period, again as described in Section 5.4.

Patients in the inhibitor subgroup will be further split by the sub-classification of inhibitor as described in Section 5.1.2.5, namely:

- Patients with high-titer inhibitors
- Patients with low-titer inhibitors that meet the clinically meaningful criteria as defined in Section 5.1.2.5
- Patients with low-titer inhibitors that do not meet the clinically meaningful criteria

For this presentation, the analysis of longitudinal data will be presented for the entire safety or efficacy periods, dichotomized as described in Section 5.4.7, i.e.:

- From start of the relevant period up to the date of the positive inhibitor (all patients in the inhibitor subgroup combined)
- From date of positive inhibitor to the end of the relevant period

The definition of a positive inhibitor and the date of onset are described in Section 5.1.2.4.

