9.4.3.3. Supporting Analyses

To support the primary analysis results, the following will also be presented, using the primary methodology.

Overall Incidence based upon ED Milestones

The overall incidence of positive inhibitor formation will be presented for all patients who have reached at least 1, 20 and 50 EDs and had at least one inhibitor test performed at or beyond this milestone.

Incidence by Titer

The incidence of positive inhibitor formation will be analysed separately for the types of inhibitor specified in Sections 5.1.2.4 and 5.1.2.5, namely:

- Patients with high-titer inhibitors
- Patients with low-titer inhibitors that meet the clinically meaningful criteria
- Patients with high-titer inhibitors or low-titer inhibitors that meet the clinically meaningful criteria
- Patients with low-titer inhibitors that do not meet the clinically meaningful criteria

These analyses will all be based upon all patients with at least 1, 10, 20 and 50 EDs.

Time to Inhibitor Development

The cumulative incidence of inhibitors over time (EDs) will be estimated using the Kaplan-Meier method. This will be presented graphically for high and low titer (CS and NCS) inhibitors, as defined in Sections 5.1.2.4 and 5.1.2.5, as well as overall CS and overall. For patients who do not have an inhibitor, follow-up time will be censored at the last ED at the time of analysis.

Additionally a summary of EDs at time of inhibitor development will be provided, again for high and low titer (CS and NCS) inhibitors as well as overall CS and overall. This will include Kaplan-Meier estimates of cumulative incidence of inhibitor development at 10, 20 and 50 EDs.

Incidence by Peak Titer

The incidence rate of high and low titer inhibitor formation will be estimated and presented for peak titers, defined as the highest titer level detected during testing, dichotomized by:

- High titer, where peak titer ≥ 5.00 BU/mL
- Low titer, where peak titer ≥ 0.60 and < 5.00 BU/mL.

These analyses will be based upon all patients with at least 1, 10, 20 and 50 EDs.

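### The inhibitor risk-factor table stops counting infection, vaccination and major surgery at the inhibitor date but sets no cut-off for patients without an inhibitor, so these factors are biased toward looking protective

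*SAP*

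**What the plan says.** SAP 6.2.2.4 sets up a two-group comparison: "The following risk factors will be summarized for patients in the inhibitor subgroup and those not". Race, family history of inhibitors and genotype are fixed at baseline. The other three factors are yes/no flags that depend on time on study:

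- infection: "TEAE of infection prior to date of inhibitor development - Y/N"
- major surgery: "Major surgery during study prior to date of inhibitor development - Y/N"
- vaccination: "as per hemophilia history data and concomitant medications prior to date of inhibitor development"

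SAP 5.1.2.4 defines the inhibitor date as the date of the first positive sample that is later confirmed. A patient who never develops an inhibitor has no such date, and 6.2.2.4 does not say where that patient's window ends.

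The closest rule is SAP 5.1.1.2. For longitudinal data split by inhibitor subgroup it says that "the safety or efficacy periods included for these groups is the entire period". For adverse events that runs to the final safety follow-up (SAP 5.4.4).

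The SAP does set an end point for the same patients in the Kaplan-Meier analysis of SAP 9.4.3.3: "For patients who do not have an inhibitor, follow-up time will be censored at the last ED at the time of analysis". Nothing comparable appears in 6.2.2.4, and SAP section 10 does not mention the point.

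**The concern.** A longer window collects more events. If an inhibitor patient's window closes at onset while the other group's stays open to the end of follow-up, the percentage flagged yes is lower in the inhibitor column even when the factor has no effect. The direction does not depend on the event rate. It needs only that inhibitors occur, on average, before the other patients' follow-up ends.

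The table is descriptive, but it concerns the study's primary safety question and is a listed output. By default it is produced at both the interim and the final analysis. A reader could take infection to be harmless or protective when it raises risk. The Kaplan-Meier analysis does not correct this, because it is presented by titer and not by risk factor.

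**Working it through.** The plan states no expected value for this table, so there is no figure to reproduce. The check asks what the table would show under known truths.

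**From the documents.** Prophylaxis is given "in the range of 25 to 65 IU/kg at 3 to 5 day intervals" (Protocol 10.2.3). Patients without an inhibitor are treated for at least 50 EDs (Protocol 7.3). About 105 patients are to be dosed (SAP 3.3). The vaccination flag includes pre-study history: SAP 6.2.2.1 lists "FVIII genotype, family history of inhibitors, vaccination within last year".

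**Assumed.** Inhibitor onset near ED 15; 1, 2 or 3 events per year; 50% already flagged for vaccination from history; major surgery at 0.05 per year; 30 inhibitor patients and 75 others.

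**Formula.** With a constant rate r, a window w in years and a shared pre-study proportion h (0 except for vaccination):

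P(yes) = 1 − (1 − h) × exp(−r × w)

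The odds ratio is the odds of yes in inhibitor patients divided by the odds in the others.

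**Windows.** At intervals of k days, ED 15 falls at 14k days and ED 50 at 49k days. For k = 3 to 5 this is 42–70 against 147–245 days. Windows of 0.15 and 0.5 year lie close to k = 4 (56 and 196 days). For a long episodic lead-in with one year of follow-up, ED 15 falls at 365 − 35k days. With k = 4 that is 225 days, or 0.62 year.

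**Worked example.** At r = 2 over 0.15 against 0.5 year, P = 1 − exp(−0.3) = 25.9% against 1 − exp(−1) = 63.2%. The odds are 0.350 and 1.718, so the odds ratio is 0.20.

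**Odds ratios with no true association:**

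| Setting | 1/year | 2/year | 3/year |
|---|---|---|---|
| 0.15 vs 0.5 year | 0.25 | 0.20 | 0.16 |
| Prophylaxis from first dose, k = 3 to 5 | 0.22–0.25 | 0.17–0.21 | 0.12–0.18 |
| Episodic lead-in, k = 4 | 0.50 | 0.38 | 0.28 |
| Episodic lead-in, k = 3 to 5 | 0.40–0.60 | 0.29–0.49 | 0.20–0.39 |
| Vaccination, h = 0.5, 0.15 vs 0.5 year | 0.58 | 0.38 | 0.27 |

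**Major surgery.** 30 × (1 − exp(−0.05 × 0.15)) = 0.2 inhibitor patients and 75 × (1 − exp(−0.05 × 0.5)) = 1.9 others are flagged.

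**With a true effect (simulation).** Each setting used 400,000 patients, 4-day intervals and 50 EDs. The inhibitor hazard was 0.35/25 per ED over the first 25 EDs, which gives about 30% inhibitors when there is no effect. The hazard was multiplied by the true ratio after the first infection. Odds ratios the table would show at 1, 2 and 3 infections per year:

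| True hazard ratio | No lead-in | Episodic lead-in |
|---|---|---|
| 2 | 0.39 / 0.31 / 0.23 | 0.68 / 0.44 / 0.26 |
| 3 | 0.57 / 0.46 / 0.35 | 1.10 / 0.72 / 0.43 |

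Separate re-runs for a true ratio of 2 gave values within about 0.06 of these; small differences come from how EDs are indexed. Truncating each patient without an inhibitor at the ED of a matched case returns about 1.0 when there is no effect and about 1.8 to 2.2 for a true ratio of 2.

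**The case against.** The strongest reply is that the SAP does not actually prescribe unequal windows. SAP 5.1.1.2 covers longitudinal data in selected tables, whereas 6.2.2.4 cross-refers to the subgroup definitions in 5.1.2.5. Table shells and programming specifications that the SAP mentions, but that are not available here, could set a window. This is fair as far as it goes: the certain defect is the missing cut-off, and the bias follows from the likely default. But if 5.1.1.2 does not apply, no rule does, and nothing in the SAP points to a matched window.

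The second reply is low stakes. The table plans no test, model or odds ratio. Adverse event listings give onset days and mark events after inhibitor development, so timing is partly recoverable. The repaired table would still be imprecise. With about 105 patients, no lead-in and 2 infections per year, the matched odds ratio has a 95% sampling range of roughly 0.36 to 2.6 under no effect and 0.89 to 5.4 for a true hazard ratio of 2. All of this stands. It limits what the table can show, but an imprecise comparison is still better than one pushed in a known direction.

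Third, infection carries most of the point. Vaccination shares its history component across both groups, and the percentage gap nearly vanishes if almost all are vaccinated at entry. Surgery may yield too few events. Both limits are accepted.

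**Conclusion.** The concern holds. SAP 6.2.2.4 leaves the window undefined for one of its two columns. Under the only rule the SAP offers for this split, infection, on-study vaccination and major surgery are biased toward looking protective.

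The direction is secure, but the size is not, because event rates and onset timing are not in the documents. Under the assumptions shown, a neutral factor has an odds ratio of about 0.12 to 0.60. One that doubles the hazard shows about 0.2 to 0.7. A strong effect can keep its direction: the lead-in case with a true ratio of 3 and 1 infection per year shows 1.10.

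Race, family history, genotype, the primary incidence and its confidence interval are unaffected. The SAP should be changed, although the trial's main result does not depend on it.

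**What to change.** Keep the present two-column table for baseline factors: race, family history, genotype and vaccination before the first dose.

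For on-study infection, vaccination and major surgery, state one window for both groups. Give each patient without an inhibitor the onset ED of a matched inhibitor case and count events only up to that ED. The SAP should say how the case is drawn (for example at random with a fixed seed) and what happens when the patient never reaches that ED (for example, a cap at the patient's own last ED).

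Alternatively, report events per ED at risk before inhibitor or censoring, restricted to the same ED range in both groups. The restriction matters because episodic EDs span more calendar time. In the lead-in case the first 14 intervals take 225 / 14 ≈ 16 days each, against 365 / 50 ≈ 7 days per ED overall.

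The cost is SAP wording and one derivation from on-study dates and EDs. Later events in patients without an inhibitor drop out of this table, and partial vaccination dates need a rule.

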6.3. Physical Examination

The number and percentage of patients with physical examination abnormalities at screening will be presented by body system. Percentages will be based on the number of patients for whom a screening physical examination is available. On-treatment physical examination findings will be listed.

6.4. Non-study Drug Medications

6.4.1. Prior and Concomitant Medications

Prior and concomitant medications relative to rFVIII Fc will be summarized for the Safety Analysis Set. Summaries will be based on the number and percentage of patients taking medications by WHODrug standardized medication text. Within each WHODrug standardized medication text a patient will be counted once even if he reported taking the medication more than once. Separate summaries will be provided for prior and concomitant medications. Medications taken after the EOS visit up to the Follow-Up visit/phone call will not be included in the summary table of concomitant medications. Two listings will be provided, one for prior and concomitant medications taken through the EOS visit and the other for medications taken after the EOS visit and prior to the Follow-Up visit/phone call.

Medications will be identified as being prior and/or concomitant based on the start and stop dates compared to the first dose of rFVIII Fc. Prior medications are all drugs and substances taken before the first rFVIII Fc dose was received. Concomitant medications are those administered during or after the first injection of rFVIII Fc while on study, or administered prior to the first administration of rFVIII Fc and ongoing at the start of rFVIII Fc administration.

Prior and concomitant medications will be characterized based on the onset and resolution dates relative to the date and time of the first dose of rFVIII Fc. Medications reported for a patient will be classified as concomitant unless they can be excluded as such, as follows:

- A medication that is started prior to the first dose of rFVIII Fc and was ongoing during and/or after the first dose of rFVIII Fc will be classified as both prior and concomitant.
- Medications with a start date after the follow-up visit will not be considered concomitant and will not be included in the summary tables.
- For partial dates, if a concomitant medication start day is missing then the medication will be assumed to be both a prior and a concomitant medication unless the start month and/or year or medication stop date can be used to determine if a medication is concomitant or prior, as follows:

- If the concomitant medication start day is missing, but the month and year are before the start month and year of the first dose of rFVIIIIFc and the concomitant medication stop date is before the start day of the first dose of rFVIIIIFc, then the medication will be classed as prior only.
- If the day of the start date is missing and the month and year are after the month and year of the first dose of rFVIIIIFc then the medication will be classed as concomitant only.
- If the month of the start date is missing and the year is before the start year of the first dose of rFVIIIIFc and the stop date is before the start date of the first dose of rFVIIIIFc, then the medication will be classed as prior only.

In this study, for patients who receive breast milk, maternal concomitant medications are also be collected at the same time points as other concomitant therapies, unless the breast milk is derived from a source other than the mother or the mother did not consent. These will be presented in a separate table, but in a similar way, to other concomitant medications.

Prior and concomitant medication will be coded using WHODrug-enhanced dictionary version from March 2017.

6.4.2. Other Therapies and Procedures

Other therapies administered and concomitant procedures performed within 30 days prior to the first dose of study drug through the end of the study will be listed only, a summary table is not planned.

6.5. Protocol Deviations

Protocol deviations will be recorded throughout the study or in the case of deviations based upon the EPD, monitored throughout the study and finalized at the end (more details in the Programmatically-Defined Protocol Deviations Criteria document). Major and minor protocol deviations/violations are to be pre-specified prior to database lock, as per the guidance provided in the study Clinical Operations Plan document.

The number of patients with major protocol deviations will be summarized for the Safety Analysis Set and also including only deviations that affect efficacy, to be identified prior to database lock. Major protocol deviations that occurred during a surgical/rehabilitation period will be presented separately in the summary. A data listing of all protocol deviations, major and minor, will be provided.

6.6. Study Drug

Study treatment is described in Section 3.1.2. Study drug administered will be listed by patient for the FAS. This will include the reason for administration (PK assessment, episodic (treatment of a bleeding episode), prophylaxis, ITI, surgery, other) date and time of administration, dose, and dosing intervals, consumption and compliance. It will also include lot number and nominal potency of the lots used.

Except for PK doses, the unit body weight dose (IU/kg) for analysis of dosing will be calculated as the total IU (nominal dose) for each injection divided by the patient's most recent weight in kg prior to the dose of study drug.

PK doses were all 25 IU/kg at the Baseline IR Visit, 50 IU/kg during the ITI regimen for IR and t_{1/2} assessments, and were calculated using the actual potency of the vial (between 80 to 125% of nominal strength) and used partial vials where necessary. Therefore PK doses in the analysis are similarly calculated using the exact number of complete and partial vials, the volume and actual potency of each vial and the patient's most recent weight.

Both types of dose are calculated as follows:

$$\text{Dose (IU/kg)} = \frac{\left(\frac{\text{Total volume administered}}{\text{Volume of vial}} \right) \times \text{Actual/Nominal Potency of Vial}}{\text{Weight (kg)}}$$

PK doses were not used for the purpose of preventing or treating bleeding and therefore the total annualized rFVIII Fc consumption will exclude the IU/kg amount that was used for PK doses. However, data collected over the time in which the PK dose was administered will be included in the safety analyses.

